1. PROGRAM SUMMARY

Please provide a brief summary of your grant project including the needs to be addressed, the services provided, and the population served.

Gentle Warriors Academy (GWA) is designed to help urban community adult fathers age 18 and older with dependent child(ren) up to 24 years of age incorporate practices and behaviors for managing the responsibilities of being parents/co-parents and partners through responsible parting, healthy marriage/relationships, economic stability activities, and grant-funded participation supports through a 40-hr/10-week cohort-based approach. These core areas are reinforced through GWA's coordinated case management process and wrap-around services, which is tailored to help address obstacles that fathers and their families face on their journeys to attaining and maintaining healthy parental and partner relationships as well as program completion.

Fathers Incorporated utilizes a skills-based curricula for its core GWA services: Next Level Fatherhood which was created and tailored by subject matter experts and Fathers Incorporated practitioners/staff to address the complex challenges and needs of urban community fathers. All curricula consist of 10 modules of learning that are designed to develop practical and comprehensive skillsets that are transferrable throughout all aspects of life.

The objectives of the Next Level Fatherhood curriculum are to: 1. Provide participants with practical skills necessary to navigate critical aspects of responsible fatherhood, healthy marriages, and personal/family economic stability; 2. Provide participants with tools that will assist them in strengthening their marriages, child engagement, and co-parenting relationships, and to provide information and resources around viable economic stability for themselves and their families; 3. Provide participants with skills necessary to making better and more informed parenting choices, to be more pro-active and less reactive, and to strengthen parental relationships; and 4. Encourage participants to become more acutely aware of how they present themselves in the lives of their children, significant others, and in the "systems" (family court, judicial court, child support, state agencies etc.) in which they have to navigate.

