Participating fathers will work with Case Managers to review the results of all assessments and to determine necessary support services through the duration of program participation. Case Managers will implement case management best practices, record case notes that document interaction/support provided to all participants and will ensure that each participant receives six hours of dedicated case management from program enrollment through completion. Certified Life Coaches will work in tandem with Case Managers to help participants obtain and reach their goals, promote, and develop their strengths, and to overcome difficult challenges, specifically within their marriages or other significant relationships, their economic viability and their parental responsibilities as identified through co-developed Individual Success Plans (ISPs).

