1.2. OUTCOME RESEARCH QUESTIONS

For each outcome research question listed above, whether a descriptive or impact design, summarize the inputs (e.g., program components, program supports, implementation features, etc.), target population (e.g., the population for which the effect will be estimated) and the outcomes (e.g., child well-being, father-child engagement, etc.) that will be examined to answer the research question(s). Comparisons for descriptive evaluations may reflect circumstances before the grant, pre-treatment, or pre-determined benchmark from other studies with similar interventions.

Research Question Number Should correspond to the number indicated in Table 1.1 above	Intervention Program component or set of activities that the evaluation will test or examine	Target Population Population for which the effect of the treatment will be estimated	Comparison What the intervention will be compared to (e.g., pre-intervention for descriptive designs)	Outcome Changes that are expected to occur as a result of the intervention	Confirmatory or Exploratory? Confirmatory: those upon which conclusions will be drawn Exploratory: those that may provide additional suggestive evidence
R1	Primary curricula (Next Level Fatherhood); Support Services (Case Management, Life Coaching);	Urban fathers who are 18+ years with children up to 24 years	Assessment of healthy parenting behavior at GWA Project enrollment.	Participants who complete primary and support services will report healthier parenting behavior	Confirmatory

	Continuous Quality Improvement (CQI) Process			one year after GWA Project enrollment.	
R2	Primary curricula (Next Level Fatherhood); Support Services (Case Management, Life Coaching); Continuous Quality Improvement (CQI) Process	Urban fathers who are 18+ years with children up to 24 years	Assessment of healthy parenting attitudes at GWA Project enrollment.	Participants who complete primary and support services will report healthier parenting attitudes one year after GWA Project enrollment.	Confirmatory

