7. SAMPLE

7.1. TARGET POPULATION(S)

For each target population identified in Section 1.2, please describe the target population(s), and explicitly state whether the population(s) differs from those who will be broadly served by the grant. Describe how the target population will be identified. Explicitly state the unit of analysis (e.g., non-residential father, unmarried couple).

Description of Target Population	How is the population different from those who will be broadly served by the grant?	How will the target population be identified?	Unit of Analysis
Urban fathers age 18 years and older with children who are up to 24 years of age	No difference, all program participants will be study participants	The sample will be identified and recruited by the program staff.	Urban fathers

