We will conduct response rate analysis for each primary outcome of interest to assess non-response bias and adjust for threats to internal validity. Using data from the Applicant Characteristics Survey, we will look at demographics (race, ethnicity, age, education level) and primary reason for joining the program among participants who fall into each of the following categories: 1) non-respondents who answered no surveys after the ACS, 2) respondents who completed the pre-survey only, 3) respondents who completed the post-survey only, and 4) respondents who completed both the pre- and follow-up survey (complete case).

Subgroup Analyses

We plan to compare data across two sets of subgroups. These are participants (fathers) whose ages range from 18-29 and those over the age of 30. We also plan to compare data across incarcerated participants and community participants.

Analytic approach

The main goal of this descriptive study is to assess pre-post change scores in the outcomes listed above among program participants before and after primary workshops. The changes will be assessed from program enrollment to one year after the enrollment (follow-up survey). We will use paired sample t-tests to assess the magnitude and significance of changes among program participants in the analytic sample for each outcome. We will adjust our p-values for multiple hypothesis testing and report the adjusted p-values in the appendix of the final report.

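### The paired t-tests ignore possible clustering by workshop cohort; if change scores correlate positively within cohort, standard errors and p-values for R1–R4 will be too small

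*SAP*

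**What the plan says.** **Test.** SAP section 1, Analytic approach: "We will use paired sample t-tests to assess the magnitude and significance of changes". P-values are then to be adjusted for multiple testing, by a method that is not named. The same paragraph sets the interval: "The changes will be assessed from program enrollment to one year after the enrollment (follow-up survey". The SAP's measure table, however, takes the R4 item from the nFORM entrance and exit surveys.

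**Delivery.** Protocol section 1 (Program Summary) describes services given "through a 40-hr/10-week cohort-based approach". Protocol section 1.2 lists continuous quality improvement as part of the intervention for every research question. Section 8.4 has program data reviewed every two weeks so that delivery can be altered promptly.

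**Unit and status.** Protocol section 7.1 defines the population as "Urban fathers age 18 years and older with children who are up to 24 years of age" and makes the individual father the unit of analysis. Section 1.2 labels R1 to R4 confirmatory, defined as "Confirmatory: those upon which conclusions will be drawn".

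**Not found.** Neither the SAP nor the protocol text available for review mentions cohort, facilitator or site clustering, an ICC, cluster-robust standard errors or a mixed model.

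**The concern.** A paired t-test is a one-sample t-test on change scores. Pairing deals with the correlation between a father's own two measurements. It does nothing about correlation between the change scores of different fathers, which the test takes to be zero.

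The documents give reasons to doubt that assumption:

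- Fathers in a cohort go through the 10-week program together.
- Study enrollment runs from April 2021 to March 2024 (Protocol section 3), and delivery is meant to be adjusted along the way. Different cohorts may therefore receive somewhat different programs.
- The sample includes incarcerated and community fathers (SAP, Subgroup Analyses). If cohorts are formed by setting, items such as hours spent with children could move together within a cohort.
- Baseline is collected at an orientation session or first workshop, and the exit survey at the last workshop (Protocol sections 8.3 and 8.4). Fathers may thus share measurement occasions as well.

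In a single-group design, a shared cohort effect on change goes straight into the variance of the mean change. At stake are confidence intervals that are too narrow and a false-positive rate above nominal on the outcomes from which conclusions will be drawn. The multiplicity adjustment does not help, because it takes the unadjusted p-values as correct.

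**Working it through.** The documents state no sample size, power, alpha, ICC or cohort size in the text available, so there is no figure of the plan's own to reproduce. What follows is a sensitivity calculation.

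**Inputs**

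- From the documents: cohort delivery; a paired t-test on individual fathers; four confirmatory outcomes.
- Assumed: two-sided alpha 0.05; m = 5 to 20 analysed fathers per cohort; ICC of change scores = 0 to 0.10.

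The low end of m allows for attrition. The SAP sample needs both entrance and exit surveys, the exit survey reaches only completers present at the last session (Protocol section 8.4), and three of the four outcomes also need the follow-up survey.

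**Formulas**

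- Design effect: DE = 1 + (m − 1) × ICC
- True SE = t-test SE × √DE
- Actual type I error = 2 × [1 − Φ(1.96 / √DE)]

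**Worked case, m = 10, ICC = 0.05.** DE = 1 + 9 × 0.05 = 1.45. √DE = 1.204. 1.96 / 1.204 = 1.628. Type I error = 2 × [1 − Φ(1.628)] = 10.4%.

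| m | ICC | DE | True SE / t-test SE | Type I error |
|---|---|---|---|---|
| any | 0 | 1.00 | 1.000 | 5.0% |
| 5 | 0.01 | 1.04 | 1.020 | 5.5% |
| 10 | 0.01 | 1.09 | 1.044 | 6.1% |
| 10 | 0.02 | 1.18 | 1.086 | 7.1% |
| 10 | 0.05 | 1.45 | 1.204 | 10.4% |
| 10 | 0.10 | 1.90 | 1.378 | 15.5% |
| 20 | 0.05 | 1.95 | 1.396 | 16.0% |
| 20 | 0.10 | 2.90 | 1.703 | 25.0% |

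**Effect on one p-value.** A t-test statistic of 2.5 gives p = 0.012. At m = 10 and ICC 0.05 the corrected statistic is 2.5 / 1.204 = 2.08, and p = 0.038.

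**Effect after multiplicity adjustment.** The SAP names no method. If it were Bonferroni over four outcomes, each test would run at 0.05 / 4 = 0.0125. At m = 10 and ICC 0.05 the actual level would be 3.8%, about three times nominal.

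**Simulation check** (10,000 replicates, 30 equal cohorts assumed):

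| m | ICC | Plain t-test | t-test on cohort means |
|---|---|---|---|
| 10 | 0 | 5.1% | 5.1% |
| 10 | 0.05 | 9.9% | 4.6% |
| 15 | 0.02 | 8.2% | 4.9% |
| 15 | 0.05 | 13.4% | 4.8% |
| 10 | −0.02 | 3.4% | 5.2% |

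The simulation agrees with the formula. Analysis at cohort level brings the error rate back to about 5%. With a slightly negative ICC the plain t-test is conservative.

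**The case against.** **The stronger reading is not shown.** A reader might infer that the standard errors and p-values for all four outcomes are too small. The documents do not support that. It needs a positive ICC of change for each outcome, and no ICC, cohort size or number of cohorts is given. At an ICC of 0 there is no error at all. This objection stands, and the point is conditional for that reason.

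**The ICC may be small.** Part of the service is individual: "each participant receives six hours of dedicated case management from program enrollment through completion", with life coaching under individual plans. Outcomes concern each father's own child and co-parent. One-year change is measured long after a 10-week program ends. All of this is fair. It applies less to R4 if that item is taken from entrance and exit surveys as the measure table says, because that interval ends with the workshops. The ICC may therefore differ by outcome.

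**Inference may be limited to the cohorts run.** The SAP calls the study descriptive. If cohort effects are treated as fixed, the inflation does not follow. But the research questions ask about significant improvement, the outcomes are confirmatory, and Protocol section 2 aims to tell practitioners whether the program design works. Those aims reach beyond the cohorts observed.

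**How cohorts map to staff and sites is not described.** This also stands. Shared facilitators or setting within a cohort is plausible but not documented, and the argument rests on cohort delivery and shared calendar time.

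**The remedy has a price.** Intervals could widen by more than a little, and nothing in the documents shows that cohort is held in the data. Both are counted under the fix.

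**Conclusion.** The omission is clear: a cohort-delivered program is analysed with a test that assumes independent fathers, and nothing in the plan checks or corrects for dependence. Whether this biases the results, and by how much, cannot be settled from the documents.

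If change scores correlate positively within cohort, and results are generalised beyond the cohorts run, standard errors and p-values for R1–R4 will be too small. With two-sided alpha assumed to be 0.05, the type I error goes from no inflation at an ICC of 0, through about 10% with 10 analysed fathers per cohort and an ICC of 0.05, to about 16% with 20 per cohort and the same ICC. Every one of these sizes rests on assumed inputs.

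This is a cheap improvement, held with moderate confidence. It is not a demonstrated error in the results for any of the four outcomes.

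**What to change.** In the SAP's Analytic approach:

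1. Carry the workshop cohort into the analysis file, with facilitator and site where known.
2. For each outcome, estimate mean change by an intercept-only regression of the change score with cohort-clustered standard errors and a small-sample correction. The point estimate is the same mean change that the paired t-test uses.
3. Take the confidence interval and the p-value from that model, and apply the multiplicity adjustment to that p-value.
4. Report the ICC of change and the number of cohorts for each outcome.
5. Show the plain paired t-test as secondary.

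No ICC is needed in advance, since the dependence is estimated from the data. A random cohort intercept is an alternative, but it reweights cohorts of unequal size and can estimate a different mean if change varies with cohort size. The clustered regression is the simpler choice.

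**Cost.** SAP wording and a few lines of R, which the SAP already names as its software. Cohort must be recorded or recovered: the SAP links files by Client ID, and Protocol section 10.2 lists only Client ID, name and date of birth as identifiers. Intervals would be about 4% wider at 10 per cohort and ICC 0.01, and about 40% wider at 20 per cohort and ICC 0.05. They would change little if the ICC is near zero. If the number of cohorts proves small, the small-sample correction matters more and precision falls further.
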